6.1 Missing Dates Imputation

For Baseline, efficacy, and safety parameters, if the day and/or month are missing, the following conventions will be used to impute the missing dates:

- 01 for missing start day
- End of month for missing end day
- January 1st for missing start month
- December 31st for missing end month

In case of partially missing AE start and stop dates, the dates will be imputed by comparing to first dose date of study medication so that the corresponding AEs will be made treatment-emergent whenever possible. If the start date of an AE is partially missing and the month is the same as the start date of a new therapy, the AE will be made treatment emergent to the new therapy.

In case of missing or partially missing study drug dosing dates, the dates will not be imputed and subjects will be treated as not receiving dose on that date.

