The information should be documented on the source documents as per "best recollection" and when possible, re-verified when the diary is returned before completing on the applicable eCRF page.

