9.0 Study Drug Exposure and Compliance

9.1 Study Drug Exposure

The duration of exposure to study drug will be summarized using the mean, standard deviation, minimum, median, and maximum for the safety population. Duration of exposure is defined for each subject as number of days since first dose of study drug through the last study drug dose date + 70 days. Study drug dose date refers to recorded dates of injections of study drug.

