9.2 Study Drug Compliance

The treatment compliance (%) of study drug will be summarized using the mean, standard deviation, minimum, median, and maximum for safety population. The compliance rate will be calculated as follows:

Compliance rate (%) = the total number of injection received/the total number of injection expected * 100

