11.2.1 Treatment-Emergent Adverse Events

Treatment-emergent AEs (TEAE) are defined as events that begin or worsen either on or after the first dose of the study medication and within 70 days after the last dose of the study drug.

Events where the onset date is the same as the study drug start date are assumed to be treatment-emergent, unless the study drug start time and the adverse event start time are collected and the adverse event start time is prior to the study drug start time. If an incomplete onset date was collected for an adverse event, the event will be assumed to be treatment-emergent unless there is other evidence that confirms that the event was not treatment-emergent (e.g., the event end date was prior to the study drug start date).

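### SAP 6.1 counts an undated final injection as not given, which can end the TEAE window and exposure 7 to 42 days early

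*SAP*

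**What the plan says.** SAP 6.1 sets the rule for dosing dates. It applies "In case of missing or partially missing study drug dosing dates", so it covers both wholly and partly unknown dates. For such an injection the instruction is that "the dates will not be imputed and subjects will be treated as not receiving dose on that date". It makes no exception for the last dose and names no other source to fall back on.

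Four other parts of the SAP depend on that date or count:
- SAP 9.1 defines exposure as the "number of days since first dose of study drug through the last study drug dose date + 70 days", and adds: "Study drug dose date refers to recorded dates of injections of study drug".
- SAP 11.2.1 counts an event as treatment-emergent if it begins or worsens on or after the first dose and "within 70 days after the last dose of the study drug".
- SAP 11.2.2.9 uses the summed exposure from SAP 9.1 as the denominator of the event rate per 100 patient-years.
- SAP 10.3 censors time to dose escalation at the last available dose date in subjects who never escalate.

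SAP 9.2 computes compliance as "the total number of injection received/the total number of injection expected * 100" and does not say whether an injection must be dated to count as received.

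For adverse events with partial dates, SAP 6.1 takes a cautious line. It imputes them "so that the corresponding AEs will be made treatment-emergent whenever possible".

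**The concern.** The rule merges two situations that the source records keep apart. Under Protocol 5.5.4, a dose that was not taken is recorded as such. Under Protocol 5.5.5, when the diary is not returned the site questions the subject about dosing, and "The information should be documented on the source documents as per" best recollection. That can leave an injection known to have been given without an exact date. SAP 6.1 then handles it like a dose not taken.

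The end of dosing is where this matters. Under Protocol Appendix G the eow doses at Weeks 34, 36 and 38 are taken at home, and no drug is given at Week 40. The last dose of a completer is therefore self-administered and recorded in a paper diary. If its date is incomplete, the previous dated injection becomes the last dose, and the 70-day window is counted from there. An event with a complete onset date late in the true window then loses its treatment-emergent status. Long-term safety is part of the primary objective.

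**Working it through.** The documents give no figure to reproduce, so the check is arithmetic on the dosing schedule.

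**Inputs**
- eow doses (Protocol Appendix G): Week 0 in clinic, 15 at home and 4 more in clinic, so 20 in all, ending at Week 38.
- ew doses: last at Week 39 (Protocol 5.5.1). A subject on ew throughout would have Weeks 0 to 39, so 40 doses.
- First dose is Day 1 (SAP 6.0); Week 40 is nominally Day 281 (SAP Table 3).
- 252 subjects enrolled (SAP 4.2).

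**Formulas**
- Dose day = 7 × week + 1.
- End of TEAE window = last dated dose day + 70. Exposure in days, counting Day 1, is the same number.
- Compliance = dated injections / expected injections, if only dated injections count as received.

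**Results for a completer**

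| Undated doses | Last dated dose | Window end and exposure | Days lost | Exposure change | Compliance if only dated doses count |
|---|---|---|---|---|---|
| eow, none | Day 267 | 337 | 0 | 0 | 20/20 = 100% |
| eow, last one | Day 253 | 323 | 14 | −4.2% | 19/20 = 95% |
| eow, last two | Day 239 | 309 | 28 | −8.3% | 18/20 = 90% |
| eow, last three | Day 225 | 295 | 42 | −12.5% | 17/20 = 85% |
| eow, one mid-study | Day 267 | 337 | 0 | 0 | 19/20 = 95% |
| ew, none | Day 274 | 344 | 0 | 0 | 40/40 = 100% |
| ew, last one | Day 267 | 337 | 7 | −2.0% | 39/40 = 97.5% |

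The window and exposure change only when the undated dose is the last, or belongs to an unbroken final run. A gap in mid-study affects compliance alone, and only under that reading of SAP 9.2.

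**Which events are exposed.** In every row the window still ends after Day 281, so events up to the nominal Week 40 visit stay treatment-emergent. The true eow window leaves 337 − 281 = 56 days after that visit. One undated dose removes 14 of these (25%), and three remove 42 (75%).

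**Rate per 100 patient-years.** If e of E events and t of T patient-years are lost, the rate goes from E/T to (E − e)/(T − t). It falls if e/E exceeds t/T and rises if it is smaller. The documents do not determine which.

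**Cohort scale.** The documents give no share of subjects with an undated last dose, so I assume 1%, 5% or 10%, and treat all 252 as eow completers. Total exposure is 252 × 337 / 365.25 = 232.5 patient-years. With 14 days lost per affected subject it becomes 232.4, 232.0 or 231.5, a fall of 0.04%, 0.21% or 0.42%.

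**The case against.** The case against is strong on frequency and scale.

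- **Safeguards.** Protocol 5.4.1 requires sites to try every route to the last-dose date and to record it on the eCRF. Doses fall on a fixed weekday within ±3 days, and dosing records are checked at each visit (Protocol 5.3.1.1). Syringes and boxes are reconciled (Protocol 5.5.6). Recollected information is to be re-verified, where possible, once the diary comes back (Protocol 5.5.5). This stands: incomplete last-dose dates should be uncommon, and a reader should not infer from the recollection provision that they are expected. The requirement in 5.4.1 sits under discontinuation, however, so its reach to completers is arguable, and the SAP does not link its rule to that eCRF date.
- **Wording of SAP 11.2.1.** It refers to the last dose, not the last dated dose. But SAP 6.1 says an undated injection is treated as not received, SAP 9.1 limits dose dates to recorded ones, and no other source is named. The shortened window is what a programmer following the text would produce.
- **Loss of events.** One might infer that adverse events are discarded. They are not. Protocol 6.4 collects events for 70 days after study drug is discontinued, and SAP 11.2.2.4 lists all pre- and post-treatment serious events and deaths. Only the treatment-emergent flag is lost. Subjects who continue on adalimumab need no 70-day call, so fewer events are likely to be captured there.
- **Conflict with the adverse event rule.** It is tempting to call the two date rules contradictory. The partial-date rule for adverse events compares with the first dose and settles the start of the window; the dosing rule affects its end. They differ in caution but do not contradict each other.

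**Conclusion.** The point holds as a minor defect. The SAP states a rule that gives a wrong last-dose date when the final injection was given but its date is incomplete. For such a completer the TEAE window and exposure shorten by 14 days (one eow dose), 7 days (one ew dose) or 42 days (last three eow doses). The 42-day figure needs three consecutive undated doses and is not the typical case. Censoring of time to dose escalation shifts in the same way.

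TEAE counts and percentages can only fall. A reader might infer that every safety measure is biased favourably; that does not follow, because the rate per 100 patient-years loses from both numerator and denominator. Nor do the documents establish that compliance is understated: that depends on reading SAP 9.2 as counting dated injections only, and lower compliance would not favour the drug.

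The number of subjects affected is unknown and probably small, and on the assumed shares total exposure changes by less than half a percent. The practical risk is that a late event in an individual subject drops out of the TEAE tables. The conclusion assumes that the TEAE window is programmed from the same last-dose date as exposure.

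**What to change.** Amend SAP 6.1 as follows:

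1. For compliance, count every injection documented as given as received, whether or not its date is complete.
2. For the end of the TEAE window and of exposure, take the last-dose date from the eCRF page that records it.
3. If that date is partial, use the latest date compatible with it. If it is wholly missing, use the scheduled date of the last injection documented as given. In either case do not go beyond the discontinuation or final visit date.

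Step 3 has to cover wholly missing dates, since an unreturned final diary would otherwise remain unresolved. The same date should serve the censoring in SAP 10.3.

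The cost is a few sentences and minor programming. Exposure may be slightly overstated in the few subjects whose date is imputed.

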6.2 Dealing with Multiple Measurements Collected on the Same Day

For efficacy related analyses other than imaging endpoints, if multiple measurements for a particular parameter are collected on the same day for the same subject, the average of those measurements will be used.

For safety related analyses, if multiple measurements are made for a particular laboratory or vital sign parameter on the same day for the same subjects, the average of the values will be used in the analyses of change from Baseline. For summaries and listings for shift from baseline and potentially significant values, all collected values within the pre-specified treatment window will be used.

7.0 Demographics, Baseline Characteristics, Medical History, and Previous/Concomitant Medications

7.1 Demographic and Baseline Characteristics

The following demographic and Study M14-115 baseline characteristics will be summarized by treatment group.

Continuous Variables:

- Age (years)
- Body weight (kg)
- Height (cm)
- Body Mass Index (kg/m²)
- Blood Pressure (systolic/diastolic) (mmHg)
- Pulse (bpm)
- Respiratory Rate (RPM)
- Temperature (°C)
- CDAI
- SFPS
- Total SES-CD
- Crohn's Disease Duration (years)
- IBDQ score
- WPAI and its components
- EQ-5D
- Abdominal Pain Rating Scale

- hs-CRP mg/L
- Fecal calprotectin µg/g

Categorical Variables:

The baseline used for the following categorical variables is defined as the baseline in Study M14-115.

- Sex (male, female)
- Race
- Ethnicity
- Age (\leq median, $>$ median)
- Age ($<$ 40, 40 to $<$ 65, 65 to $<$ 75, \geq 75)
- Baseline fecal calprotectin (\leq median, $>$ median)
- Baseline fecal calprotectin (\leq 250 µg/g, $>$ 250 µg/g)
- hs-CRP at Baseline ($<$ 10 and \geq 10 mg/L)
- hs-CRP at Baseline (\leq median, $>$ median)
- Baseline corticosteroid use (yes, no)
- Baseline immunosuppressant use (yes, no)
- Crohn's disease severity (CDAI \leq 300, $>$ 300) at Baseline
- Baseline CDAI (\leq median, $>$ median)
- Baseline SES-CD (\leq median, $>$ median)
- Prior infliximab use (yes, no)
- Weight (\leq median, $>$ median)
- Baseline albumin (\leq median, $>$ median)
- Disease duration (\leq median, $>$ median)
- Disease duration (\leq 3 years, $>$ 3 years)
- Tobacco use (user, ex-user, never used, unknown)
- Alcohol use (drinker, ex-drinker, non-drinker, unknown)
- Region (US, ex-US)

- Study M14-115 induction dose (higher, standard) [will be performed after Study M14-115 database lock.]

Demographic and Baseline characteristics will be summarized with descriptive statistics for the ITT analysis set. The number of non-missing observations, mean, standard deviation, median, minimum and maximum will be summarized for continuous variables. The counts and percentages will be summarized for categorical variables.

7.2 Medical/Surgical History

Medical/Surgical history data will be summarized using body systems and conditions/diagnoses as captured on the CRF. The body systems will be presented in alphabetical order and the conditions/diagnoses will be presented in alphabetical order within each body system. Subjects reporting more than one condition/diagnosis within a body system will be counted only once for that body system.

7.3 Prior and Concomitant Medications

The number and percent of subjects who received a prior or concomitant medication will be tabulated by the generic name assigned by the most current version of the World Health Organization (WHO) Drug Dictionary in alphabetical order for prior and concomitant medications, respectively.

A prior medication is defined as any medication taken prior to the first dose of study drug of Study M14-115 and collected in the CRF. A concomitant medication is defined as any medication other than study drug that (1) was started prior to the first dose of study drug of Study M14-347 and continued to be taken after the first dose of study drug or (2) was started after the first dose of study drug, but was not started after the last dose of study drug. A particular medication may be classified as "prior" or "concomitant" or "both."

The prior and concomitant medications will be summarized for ITT analysis set.

Concomitant medications at baseline include prior medications that have a start date before first dose of study drug and are ongoing or have a stop date after first dose of study drug.

The number and percent of subjects using Crohn's disease specific medications (including corticosteroids [$0, \leq 10 \text{ mg}, \leq 20 \text{ mg}, \text{ or } \leq 30 \text{ mg}$ prednisone equivalents], aminosalicylates, immunomodulators [defined as azathioprine, mercaptopurine, or methotrexate], and antibiotics) prior to Study M14-115 Baseline, and at Study M14-115 Baseline will be tabulated. In addition, the number and percent of subjects using infliximab at any time prior to Study M14-115 Baseline will be tabulated.

8.0 Patient Disposition

The number of subjects will be tabulated by country, investigator site and overall for the following sets:

- ITT analysis set
- Safety analysis set
- Subjects who completed study
- Subjects who prematurely discontinued study drug

In addition, the number and percentage of subjects who discontinued study drug will be summarized by primary reason and by any reason as recorded on the eCRF:

- Adverse event (AE)
- Withdrew consent
- Lost to follow-up
- Lack of efficacy
- Requires alternative (or prohibited) therapy
- Subject non-compliance
- Other

Subjects may have more than one reason for discontinuing study drug, but they will be counted once for the total number of discontinuations. Subjects have only one primary reason for discontinuing study drug or discontinuing from the study.

9.0 Study Drug Exposure and Compliance

9.1 Study Drug Exposure

The duration of exposure to study drug will be summarized using the mean, standard deviation, minimum, median, and maximum for the safety population. Duration of exposure is defined for each subject as number of days since first dose of study drug through the last study drug dose date + 70 days. Study drug dose date refers to recorded dates of injections of study drug.

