A final phone call will be made to the subject approximately 70 days after the last dose of study drug to determine the status of any ongoing AEs/SAEs or the occurrence of any new AEs/SAEs. The 70-day follow-up phone call will not be required for any subject who initiates commercial adalimumab.

All attempts must be made to determine the date of the last dose of study drug and the primary reason for premature discontinuation. The information will be recorded on the appropriate eCRF page.

For subjects who are considered lost to follow-up, reasonable attempts must be made to obtain information on the final status of the subject. At a minimum, two phone calls must be made and one certified letter must be sent.

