6.4 Adverse Event Collection Period

All adverse events including ongoing AEs from Study M14-115, and reported from the time of study drug administration until 70 days following discontinuation of study drug administration have elapsed will be collected, whether solicited or spontaneously reported by the subject. In addition, SAEs will be collected from the time the subject signed the study-specific informed consent. Adverse event information will be collected and recorded on the appropriate eCRFs.

[figure not shown]
Subjects will be contacted approximately 70 days following study drug discontinuation for an assessment of any new or ongoing AEs, except those subjects who continue on adalimumab therapy after the end of study participation. These subjects are not required to complete the 70-day follow-up and any new AEs should be reported through the mechanism used for all post-marketing adverse experiences. The 70-day follow-up phone call will be recorded in source document only and confirmation of the contact will be faxed to AbbVie ([Appendix J](#)).

All AEs identified to AbbVie from the 70-day follow-up phone call will be collected as source data to be evaluated and reported ([Figure 3](#)). Thus, all SAEs and nonserious AEs as defined by AbbVie, reported during the 70-day follow-up phone call must be captured

in the clinical database. The end of trial is the last subject contact, i.e., the 70 day follow-up call.

Adverse event information will be collected as shown in [Figure 3](#).

Figure 3. Adverse Event Collection

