Subjects might discontinue adalimumab treatment at any time during study participation (Section 5.4). Subjects would be discontinued from the study if they withdraw consent or if they were deemed unsuitable to continue for any reason by the Investigator. Subjects who ended study participation early would have a PD visit. All subjects were to have a follow-up phone call approximately 70 days after the last administration of study drug to obtain information on any new or ongoing adverse events (AEs). The 70-day follow-up phone call would not be required for any subject who initiated commercial adalimumab.

Clinical evaluation was completed at each study visit. See activities outlined in [Table 2](#).

Throughout the study, subjects were only allowed to change the dosage of CD-specific concomitant medications as specified below:

- Immunosuppressant doses might be decreased or terminated in the event of moderate-to-severe treatment-related toxicities.
- Subjects who were taking corticosteroid therapy at Baseline of Study M14-115 should continue the steroid taper initiated during Study M14-115. Increases in steroid doses back to the dose used at Baseline of Study M14-115 to manage inadequately controlled CD-related symptoms might be undertaken at the Investigator's discretion in subjects who were receiving adalimumab 40 mg eow.

For subjects taking adalimumab 40 mg eow, adalimumab dose escalation (for subjects who meet inadequate response criteria) were to be considered in lieu of increases in the steroid dose.

Table 2. Study Activities

| Activity | Baseline (Week 0) ^a | Week 8 | Week 16 | Week 24 | Week 32 | Week 40/ Premature Discontinuation | Unscheduled Visit ^k | 70-Day Follow-Up Call ^l |
|---|-----------------------------------|--------|---------|---------|---------|--|-----------------------------------|--|
| Informed Consent | X | | | | | | | |
| Inclusion/Exclusion ^b | X | | | | | | | |
| Medical/Surgery History Update ^b | X | | | | | | | |
| Previous and Concomitant Medication Update ^b | X | X | X | X | X | X | X | X |
| Vital Signs | X ^a | X | X | X | X | X | X | X |
| Endoscopy ^c | X ^a | | | | | X | | |
| SES-CD Score | X ^a | | | | | X | | |
| Physical Examination ^d | X ^a | X | X | X | X | X | X | X |
| Urinalysis ^e | X ^a | X | X | X | X | X | X | X |
| Pregnancy Test ^f | X ^a | | | | | X | | |
| Chemistry and Hematology ^h | X ^a | X | X | X | X | X | X | X |
| hs-CRP | X ^a | X | X | X | X | X | X | X |

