- k. Visits for dispensing new study drug in case of temperature excursion, loss, damage, or dose escalation are not considered an Unscheduled Visit. In addition, visits to retest a lab will not be considered an Unscheduled Visit. Unscheduled visits can be used for situations including the following: For evaluation and assessment of the subject, to evaluate a subject who meets criteria for inadequate response as outlined in [Table 1](#), to collect samples to determine hs-CRP in those subjects, and to collect PK samples for a change in adalimumab dosing.
- l. Subjects will be contacted 70 days following study drug discontinuation for an assessment of any new or ongoing AEs, except those subjects who continue on commercial adalimumab therapy after the end of study participation.
- m. Sites will review the electronic diary utilized and collected from Week 12 of Study M14-115 to obtain the number of liquid or very soft stools, abdominal pain rating, general well-being and adalimumab dosing information. A new paper subject diary will be dispensed to subjects at Baseline. All subjects should complete their subject diary on a daily basis throughout the entire study, including if and when hospitalized whenever possible. The diary will be reviewed by site personnel with the subject at each visit and collected at the Final/PD visit.
- n. For patients in Ukraine only. Chest x-ray should be performed up to two weeks prior to the Week 24 visit, as a screening measure for newly developed/reactivated TB. In case diagnosis of TB is established following further assessments, such patients should be immediately discontinued from the study (as a consequence of diagnosis of TB). Procedures as per Section 5.4.1 "Discontinuation of Individual Subjects" should be applied in such cases.

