11.2.2.9 Adverse Events by 100 Patient Years

The event rates per 100 patient years of exposure to study drug will be presented for TEAE overviews and for TEAEs SOC and PT where the number of events will be used as the numerator.

$$\frac{\text{Number of TEAEs}}{\text{Total Patient Years}} \times 100$$

where total patient years is defined as the sum of the study drug exposure of all subjects, as defined in an earlier section, normalized by 365.25, and rounded to 1 decimal place.

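### The TEAE rate per 100 patient-years counts 70 days after the last dose for every subject, including those whose AEs are not solicited over that time; for these subjects it is biased low, by an amount the documents do not fix

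*SAP*

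**What the plan says.** **Denominator.** SAP 9.1 (Study Drug Exposure) gives every subject the "number of days since first dose of study drug through the last study drug dose date + 70 days". SAP 11.2.2.9 (Adverse Events by 100 Patient Years) then states that "total patient years is defined as the sum of the study drug exposure of all subjects", divided by 365.25. Neither section shortens exposure for a subject whose follow-up ended sooner.

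**Numerator.** SAP 11.2.1 counts an event as treatment-emergent up to 70 days after the last dose. Protocol 6.4 plans collection to match: AEs "until 70 days following discontinuation of study drug administration have elapsed will be collected", solicited or spontaneous.

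**Exemption.** SAP 4.2 says: "The 70-day follow-up phone call would not be required for any subject who initiated commercial adalimumab". Note l to SAP Table 2 repeats it: subjects are contacted at 70 days "except those subjects who continue on commercial adalimumab therapy after the end of study participation". Protocol 6.4 says where their events go: "These subjects are not required to complete the 70-day follow-up and any new AEs should be reported through the mechanism used for all post-marketing" events.

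**Subjects not reached.** For subjects considered lost, Protocol 5.4.1 requires attempts to establish final status: "At a minimum, two phone calls must be made and one certified letter must be sent". The call form in Protocol Appendix J has its own box for a subject who gave no information or could not be spoken to after at least one attempt. The two rules set different minimum efforts, and both allow for a subject who is never reached.

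**Record of the call.** Under Protocol 6.4 the call "will be recorded in source document only and confirmation of the contact will be faxed" to the sponsor.

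**The concern.** A rate per 100 patient-years needs events and person-time to cover the same interval. For a subject who moves to commercial adalimumab, the 70 days stay in the denominator while the protocol directs new events outside study collection. An event in that interval still meets the TEAE definition, but nobody in the study asks for it. For a subject not reached by the call, the days count and the events are not solicited. A collection gap of this kind can only lower the numerator against a fixed denominator.

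Safety is part of the primary objective, and 11.2.2.9 is the only exposure-adjusted AE summary planned. The exempt group is foreseeable: Protocol 3.3 lists Crohn's disease among the approved indications, and Appendix J has a box for continuing adalimumab. No planned output would show how large it is. SAP 8.0 does not tabulate completion of the call, and the concomitant-medication definition in SAP 7.3 leaves out drugs started after the last study dose.

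**Working it through.** The documents give no TEAE rate, no patient-year total and no share of subjects without the call, so there is no stated figure to reproduce. What follows is person-time arithmetic over a range.

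**Inputs**
- Last dose: Week 38 on every-other-week dosing (eow), Week 39 on weekly dosing (ew) (Protocol 5.5.1).
- Nominal day = 7 × week + 1, which agrees with SAP Table 3 (Week 40 = Day 281). Week 38 is Day 267 and Week 39 is Day 274.
- Premature discontinuation (PD) visit: within 2 weeks of the last dose (Protocol 5.4.1).
- Dose and visit windows: ±3 days each (Protocol 5.1 and 5.3.1.1).
- Enrolled: 252 (SAP 4.2).
- Share unfollowed, p: not in the documents; assumed from 0 to 100%.

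**One unfollowed subject.** Counted days E = last-dose day + 70. Days outside solicited collection u = E − day of last visit.
- eow completer: E = 267 + 70 = 337; u = 337 − 281 = 56; 56/337 = 16.6%.
- ew completer: E = 274 + 70 = 344; u = 344 − 281 = 63; 63/344 = 18.3%.
- ew completer at the window limits (dose on Day 277, visit on Day 278): E = 347; u = 69; 69/347 = 19.9%.
- Last dose Week 24 (Day 169), PD visit 14 days later: E = 239; u = 239 − 183 = 56; 56/239 = 23.4%.
- Last dose Week 8 (Day 57), PD visit 14 days later: E = 127; u = 127 − 71 = 56; 56/127 = 44.1%.

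**Whole study, illustrated with all 252 as eow completers**
- Planned person-time: 252 × 337/365.25 = 232.5 patient-years.
- Person-time to the last visit: 252 × 281/365.25 = 193.9. Difference: 38.6.
- Excess at share p: 252 × p × 56/365.25 = 0, 9.7, 19.3 and 38.6 patient-years at p = 0, 25, 50 and 100%.
- Understatement of the rate, with no capture after the last visit and a constant AE rate: p × 56/337 = 0, 4.2, 8.3 and 16.6%.
- The same for ew completers: p × 63/344 = 0, 4.6, 9.2 and 18.3%.

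**Sensitivity to the assumptions (eow)**
- If half of the later events are reported spontaneously: p × 0.5 × 56/337 = 0, 2.1, 4.2 and 8.3%.
- If the AE rate halves after the last visit, with everyone unfollowed: expected events are proportional to 281 + 28 = 309 and captured events to 281, so the shortfall is 28/309 = 9.1% instead of 16.6%.
- If 30% take their last dose at Week 16 (Day 113) with a PD visit 14 days later: mean counted days = 0.7 × 337 + 0.3 × 183 = 290.8, and p × 56/290.8 = 4.8, 9.6 and 19.3% at p = 25, 50 and 100%.

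**The case against.** The strongest reply is that the rule is coherent. The 70-day extension agrees with the TEAE definition and with the planned collection window, so for a followed subject numerator and denominator correspond. That stands: a reader might infer that the extra 70 days inflate the denominator for everyone, and the documents do not support that.

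The size is also open. The unfollowed share may be zero. Protocol 6.4 accepts spontaneous reports within the 70 days, so a reader who infers that unfollowed subjects yield no events after the last visit goes further than the text. The percentages equal the shortfall against the true rate only if the AE rate stays constant. Nor is 18.3% a ceiling for completers, since the dose and visit windows alone allow 19.9%. All of this stands.

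The affected output is one descriptive summary in a single-arm study. SAP 11.2 bases AE analyses generally on numbers of patients, and those tables do not use this denominator, although their counts can also miss uncollected events. No comparison between arms is distorted. That limits the weight of the point.

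Finally, a rate cut at the last visit removes observed time from followed subjects too. With 252 eow completers it drops 38.6 patient-years even if every call was completed, so a gap between the two rates does not by itself show under-collection. This is correct, and it is why the count of subjects without the call belongs in the fix. None of these points supplies a passage that truncates person-time for exempt or unreached subjects.

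**Conclusion.** The point holds, conditionally. As written, the plan gives every subject person-time to 70 days after the last dose, while the protocol exempts one identifiable group from solicited follow-up over that time and may fail to reach others. For those subjects the rate is biased low; for followed subjects it is not.

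The size cannot be fixed from the documents. Under the nominal-day, no-capture, constant-rate assumptions, the understatement among eow completers runs from 0 to 16.6% as the unfollowed share runs from 0 to 100%. Spontaneous reporting or a falling AE rate makes it smaller; early stopping, weekly dosing or use of the visit and dose windows makes it larger. A reader might infer that the reported rates will be about 17 to 18% too low. That would need every subject to be unfollowed and no later event to be reported, and nothing in the documents says so.

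The SAP should be changed, because the correction is cheap and no planned output reveals the problem. Confidence in the size is no more than moderate.

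**What to change.** Keep the planned +70-day rate and the TEAE definition. Make three additions to SAP 11.2.2.9:

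1. A second rate, for both the overview and the SOC/PT tables, in which person-time and counted TEAEs both end, for every subject, at the earlier of last dose + 70 days and the last study visit. Define that visit as Week 40/PD or, if it was not attended, the last scheduled visit attended. One rule for all keeps the cut-off independent of whether an event is reported later.
2. The number of subjects without a completed 70-day call, by reason (commercial adalimumab, not reached), taken from the faxed Appendix J forms. A spontaneous report should not count as a completed call.
3. A footnote that the two rates may also differ because the AE rate changes after the last dose.

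All SAEs and deaths within 70 days stay in the main tables and listings.

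The cost is SAP wording, one date derived from visit dates already in the database, a few extra tables, and keying one field from the faxed forms. The downside is that events after the last visit are left out of the added rate, and of that rate only.
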